The study is planned to be divided into four periods as illustrated in Figure 4. The only clinical measures to occur from the beginning of Period I are the StepWatch, Patient Journal, and Socket Comfort Score. After enrollment, the subject will spend 8 weeks (+/-2 weeks) using their own energy storage and return foot. Informed consent, demographic information, general health information, and adverse events will be collected during this period. After enrollment, the subject will be randomized to Revo, Taleo (if a transfemoral amputee), or the Proflex XC (if a transtibial amputee).

Period II – Period IV

Baseline measures are taken just prior to Period II. After the first 8 week follow up, the subject will crossover to the second comparator. After the second 8 week follow up, the subject will crossover to control. During Period IV, assessments will be repeated as in baseline. Table 2 summarizes the assessments and order of events.

[figure not shown]

Figure 4 Study Periods and Visits

Table 2 Assessments by Period and Study Visit

Period I (Control)			Period II (Revo/ Comparative)	Period III (Revo/ Comparative)	Period IV (Control)
	Visit 1	Visit 2	Visit 3	Visit 4	Visit 5
Measurement	Enrollment	Baseline 8 ± 2 weeks	Period II Follow up 8 ± 2 weeks	Period III Follow up 8 ± 2 weeks	Period IV Follow up 8 ± 2 weeks
Demographics / General Health	X				
SCS	X	X	X	X	X
ABC (extended)		X	X	X	X
PLUS-M		X	X	X	X
PROMIS-F (7a)		X	X	X	X
TAPES-FUN + TAPES-AR		X	X	X	X
EQ-5D-5L		X	X	X	X
6 Minute Walk Test (incl. BORG RPE and continuous HR)		X	X	X	X
Foot Preference Questionnaire					X
Patient Journal (incl. Pain Interference)	X	X	X	X	X
Step Count*	X	X	X	X	X
Adverse Events	X	X	X	X	X
Fitting with prosthetic foot for subsequent Period		X	X	X	

* Subject is fitted with StepWatch at previous visit so that the data may be collected prior to the following visit, this process starts at enrollment

Objectives

Safety

Safety Objectives

1. To characterize all device-related adverse events, stumbles, and falls experienced by subjects in the study by frequency and severity.

Effectiveness

Primary Efficacy Objectives

1. To characterize perception of mobility as measured by the PLUS-M while wearing the Revo-M compared to the everyday feet.
2. To characterize the level of activity restrictions as measured by the Trinity Amputation and Prosthesis Experience Scales Activity Restrictions subscale (TAPES-AR) while wearing the Revo-M compared to the everyday feet.

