The fittings during Period II and Period III are determined at random and according to amputation level. Subjects will be randomized to start with either the Revo (regardless of amputation level) or the comparative foot: Taleo if TF or KD, Proflex XC if TT. After completing Period II with the assigned foot, subjects will cross over to be fit with either the Revo, if starting with the comparative foot or the comparative foot if starting with the Revo.

Fitting process for the Revo-M investigational foot

The Revo prosthetic foot has several components which have different mechanical characteristics to allow the foot to be tailored to the patient. Subjects will complete several walking trials to determine the optimal configuration.

Fitting process for the comparative feet: Taleo and ProFlex XC

The Taleo is customizable with heel wedges that come in three different stiffnesses (soft, medium and hard). The CPO may give the subjects the opportunity to try each wedge to determine which is best.

ProFlex XC does not have any customizable components, so no configuration process is required.

Home-use Periods

Subjects will have four home-use periods during the study approximately 8 weeks in duration as shown in Figure 4 above. Prior to each home-use period, subjects will be fitted with the assigned foot and be given a Patient Journal and a StepWatch activity monitor. The Patient Journals will be completed weekly for the duration of the home-use period. The StepWatch will be worn for approximately one month and then mailed back to the clinical site. At the end of the home-use period, subjects will return to the site for a follow-up visit for assessments (see Clinical Tests & Measures for test descriptions).

Clinical Tests & Measures

Data collection for the following clinical functional assessments will be collected on eCRFs. Several questionnaires and two performance based measures will be used in the study.

For an overview of the assessments required by visit, see Table 2.

Activity monitoring (daily step counts)

The StepWatch will be used for activity monitoring to collect daily step counts during the first month of each home-use period.

Six-minute walk test (6minWT)

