All training will be documented using training records including the elements of training completed, the trainers that delivered the training and the signatures of the participants. Site initiation visits or conference calls may be made by a Sponsor-appointed Monitor to review the Study Protocol and documentation requirements with the Investigator and clinic support staff involved in the study. The Sponsor will then determine if additional center-specific training is needed and will ensure that all researchers involved in the project have adequate training. Study activities may only be performed once the Sponsor confirms activation of the investigational site.

In addition to training, at a minimum, the following documentation must be in place at the investigational site before patient enrollment begins:

- Current Investigator's and Sub-Investigator's CVs
- Signed study agreement
- Completed training in human research subject protection or an overview of Good Clinical Practice if required by the IRB.
- IRB approval letter for the Study Protocol and amendment(s)
- Patient Informed Consent approved by both the IRB and Otto Bock Healthcare Products GmbH

Adverse Events

Adverse Event Definition

An adverse event is any untoward medical occurrence in a patient. An underlying disease or symptoms associated with the underlying disease that were present prior to the fitting of study devices are not reportable. However, any increase in severity of the underlying disease or symptoms since a study fitting is to be reported as an adverse event. If an adverse event leads to multiple outcomes that sequentially worsen during the course of the study, the worst event is reported. For example, skin irritation leading to a wound infection would be reported as infection.

Adverse Event Reporting

Once a subject is enrolled, all adverse events must be reported until the subject is withdrawn or is terminated from the study.

Adverse Event Adjudication

Events will be adjudicated per the definitions below.

Serious Adverse Event

A Serious Adverse Event (SAE) is an Adverse Event that:

1. led to a death;
2. led to a serious deterioration in the health of the patient that
 - results in a life-threatening illness or injury;
 - results in a permanent impairment of a body structure or a body function;
 - requires hospitalization or prolongation of existing hospitalization;

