The sample size for the study will be a minimum of 24 existing ESR users. A sample size of 22 subjects is required to provide 80% power to detect a difference of 5 points on the PLUS-M scale using Wilcoxon's matched pairs signed ranks test and alpha of 0.05. A standard deviation of 7.7 was used to calculate the sample size. The TAPES-AR endpoint requires 21 subjects to achieve the same level of

power using a difference of 0.2 and standard deviation of 0.3. The maximum number of subjects allowed in the feasibility study was increased to 30 to allow for early study exit and/or missing data.

Interim analysis and adaptive study design

This investigation will make use of an adaptive study design. An interim analysis will be performed after all eligible patients (n=24) have completed the second study period (Period II). After the interim analysis, it will be decided whether (1) the assumptions regarding expected observed differences and standard deviations for the primary objectives are confirmed, (2) adjustments must be made in the sample size to ensure 80% power to achieve the study objectives or (3) the study must be terminated for futility. The interim analysis will be performed by an independent statistician. Review of the results and a decision on the different options will be determined by the Sponsor.

It is the intention of the Sponsor that this study would be a part of an adaptive, seamless study design in which, in the case that the feasibility study successfully achieves the primary objectives, a pivotal trial may follow with an increase in enrollment to allow for adequate statistical power to address both primary and secondary objectives. The final analysis of the pivotal trial would use data from subjects enrolled before and after the adaptation. Sample size calculations for the pivotal trial would be based on observed differences and standard deviations in outcomes measures from the feasibility study.

Hypothesis

It is expected that subjects will demonstrate better outcomes on primary and secondary endpoint measures with the Revo-M compared to their everyday feet.

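### Adverse-event reporting stops at withdrawal or termination with no follow-up of open events, so the final severity or seriousness of an event that ends participation can be missed, on any foot

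*Combined protocol and SAP*

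**What the plan says.** - **Reporting window.** Under Adverse Event Reporting, once a subject is enrolled "all adverse events must be reported until the subject is withdrawn or is terminated from the study". The rule does not depend on the foot worn.
- **Worsening events.** Under Adverse Event Definition: "If an adverse event leads to multiple outcomes that sequentially worsen during the course of the study, the worst event is reported". The section's own example is a skin irritation that becomes a wound infection and is reported as the infection.
- **Seriousness.** The Serious Adverse Event criteria rest on outcomes: death, life-threatening illness or injury, permanent impairment, hospitalization, intervention to avert permanent impairment, and fetal harm.
- **Severity.** The top grade in Table 4 depends on whether daily activity was interrupted and treatment was needed.
- **Objective.** The safety objective is "To characterize all device-related adverse events, stumbles, and falls experienced by subjects in the study by frequency and severity". No between-foot safety test is planned.
- **Early exit.** Under Sample Size, the maximum enrollment "was increased to 30 to allow for early study exit and/or missing data". No exit rate is given.
- **Schedule.** "Subjects will have four home-use periods during the study approximately 8 weeks in duration as shown in Figure 4 above". The everyday foot is worn in Period I and again in Period IV; the Revo-M is worn in Period II or Period III, in random order.

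**The concern.** The plan classifies an event partly by what happens after onset, but it stops collecting information at exit. For a subject who stays in the study the two rules fit together. For a subject whose event is the reason for leaving they do not: the record closes while the outcome is still open. An irritation reported at exit that becomes an infection a week later need never be recorded as an infection. A fall injury that leads to surgery after exit need never become a serious event.

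These may be among the most informative safety events in a feasibility study of a new foot. The section on adaptive design also intends to carry these subjects' data into the final analysis of a possible pivotal trial, so a gap left here could persist.

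**Working it through.** The plan states no figure on this point. Its sample sizes do not bear on it. The check is therefore a reading of the rules together, followed by simple arithmetic on whether the rule treats the feet differently.

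**1. Is there another route by which a later outcome would be recorded?**

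- Patient Journal: completed weekly during the home-use periods. No journal is provided for after exit.
- Table 5 (Investigator Reports): the clock starts when the investigator learns of the event, and no withdrawal cut-off is stated. It covers only unanticipated device effects and sets up no contact through which the site would learn of one. Harms already in the risk table, most of which list injury, are anticipated.
- Risks and Minimization of Risks: a subject with a technical problem stops using the prosthesis and contacts the site. This concerns subjects still in the study.
- Time Period: data collection ends with Period IV, apart from an optional 6-month continuation on the Revo-M.

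None of these follows an event open at exit.

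**2. Does the rule by itself favor one foot?**

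Inputs: four periods of length L = 8 weeks (Home-use Periods), range 6 to 10 from the ±2-week windows. Period I is on the everyday foot ("After enrollment, the subject will spend 8 weeks (+/-2 weeks) using their own energy storage and return foot"), and so is Period IV ("After the second 8 week follow up, the subject will crossover to control"). For the order: "Subjects will be randomized to start with either the Revo (regardless of amputation level) or the comparative foot". The ratio is not stated. I assume 1:1, onset spread evenly within periods, and equal weight for the two periods of each foot.

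For a completer, an event in period p has between (4 − p)L and (5 − p)L weeks of follow-up left, mean (4.5 − p)L. At L = 8:

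| Period | Foot | Weeks left | Mean |
|---|---|---|---|
| I | everyday | 24–32 | 28 |
| II | Revo-M if first | 16–24 | 20 |
| III | Revo-M if second | 8–16 | 12 |
| IV | everyday | 0–8 | 4 |

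- Everyday foot: (28 + 4)/2 = 16 weeks.
- Revo-M: (20 + 12)/2 = 16 weeks.
- At L = 6: (21 + 3)/2 = 12 and (15 + 9)/2 = 12.
- At L = 10: (35 + 5)/2 = 20 and (25 + 15)/2 = 20.

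Among completers the mean follow-up is the same for both feet. The shortest windows, 0 to 8 weeks in Period IV, belong to the everyday foot. Events open at completion are therefore cut off as well, and a repair limited to withdrawals would leave that gap.

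**3. When would a difference between feet arise?**

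Only if exit after an event is more frequent on one foot. Suppose a share f of Revo-M events ends in immediate withdrawal and no everyday-foot event does. Mean Revo-M follow-up is then 16(1 − f):

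- f = 5%: 15.2 weeks against 16
- f = 10%: 14.4 against 16
- f = 20%: 12.8 against 16

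With equal exit shares the means are equal. These values of f are illustrations; the documents give none. The reserve of 30 − 24 = 6 places covers any early exit or missing data, on any foot, so it is not an estimate of event-driven exits.

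**The case against.** The strongest case on the other side is that this is a narrow wording gap with limited consequences.

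- An injury bad enough to end participation may already meet the top grade in Table 4. This stands for some events. It does not help when treatment starts after exit, or for seriousness, which needs an outcome.
- The worst-outcome rule refers to the course of the study, which need not mean the subject's own participation. That is a fair reading, but with reporting ended and no contact planned, the later outcome would reach the record only by chance.
- Stopping a foot is not defined as leaving the study, so a subject might come off a foot and remain under reporting. This stands and narrows the problem to true exits. The protocol does not, however, describe a path for permanently stopping a study foot while staying in follow-up.
- The safety objective is descriptive and limited to device-related events. The remark on comparative safety under Benefits is a statement of possible benefit, not a planned test. This stands and limits what is at stake.

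A reader might infer more: that an event driving a subject off the Revo-M gets 0 weeks of follow-up while a Period I event on the everyday foot gets about 24, so that Revo-M severity is understated. The documents do not support this. That contrast sets a subject who withdraws against one who completes. A Period I subject who withdraws is cut off in the same way, and a Revo-M event without withdrawal has 8 to 24 weeks left. It also leaves out Period IV. Nor can the six reserve places be turned into a percentage of subjects with unfollowed study-foot events.

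**Conclusion.** The gap is real: reporting ends at exit, no other provision follows open events, and the plan's own classifications need later information. The final severity or seriousness of an event that ends participation can be missed on any foot, and the same holds for an event open when Period IV ends.

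Its size is unknown, because the number of event-driven exits and the share of events that worsen afterward are not given. With at most 30 subjects, one or two such events could visibly change a severity table. If event-driven exits turn out to be more frequent on the Revo-M and some of those events worsen after exit, its severity profile would look milder than it was. Both conditions are assumptions, and the bias is not shown. The equality of 16 weeks in completers rests on the even-onset, equal-weight and 1:1 assumptions. The gap itself rests on none of them.

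This is a cheap improvement to the primary safety objective, and it does not depend on which foot would gain.

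**What to change.** Change the rule under Adverse Event Reporting as follows:

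- Every adverse event open when a subject leaves the study for any reason (withdrawal, termination or completion of Period IV) is followed by phone, unless the subject refuses contact.
- Follow-up lasts until the event resolves or a fixed window ends, whichever is first. The window is the same for all feet, for example 8 + 2 weeks. It should not be open-ended, and it must include completers, or the repair would itself treat the feet unequally.
- Final severity, seriousness and outcome are recorded on the existing Adverse Event form and coded to the foot worn at onset.
- The existing Study Termination form records whether an event caused the exit and on which foot.
- The analysis lists event-related exits by foot, so that a reader can judge whether exits differ.

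The cost is protocol wording with the written IRB approval that any change needs, a few items on existing forms, and a phone contact or two per affected subject by existing site staff. The downside is slightly longer contact after exit. Subjects who refuse contact will still be unobserved, and their number by foot should be stated. No added subjects or clinic visits are needed.

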Sponsor Responsibilities	28
Investigator Responsibilities	28
Records and Reports.....	28
Investigator Reports.....	29
Sponsor Records	29
Sponsor Reports.....	30
Monitoring procedures	30
Study monitors.....	30
Site Visits	30
Monitoring Reports	31
Study Discontinuation or Termination.....	31
Investigational Site Termination.....	31
Premature Discontinuation of the study	31
Ethical Statement.....	31
Institutional Review Board (IRB)	31
Ethical conduct of the study	32
Disclosure of data and publication policy	32
Disclosure of data	32
Publication policy	32
Contact information	33
Contracts, finances	33
Bibliography	34

Clinical Study Summary

Title	Prospective, feasibility study to evaluate performance, patient benefits, and acceptance of a new energy storage and return prosthetic foot
Purpose	To characterize differences in performance and patient reported outcomes between the Taleo, Proflex XC, and the new Revo prosthetic foot.
Design	A prospective, interventional, multicenter pilot study
Co-Sponsors	Ottobock SE & Co. KGaA (Germany) Otto Bock HealthCare LP (United States)
Control	Current Energy Storing and Return prosthetic foot
Study Devices	Revo-M, Taleo, and ProFlex XC prosthetic feet
Enrollment	Up to 30 K3 subjects; at least 12 transtibial and 12 transfemoral
Clinical Sites	Up to 5 sites in the United States
Primary Safety Objective	To characterize all device-related adverse events, stumbles, and falls experienced by subjects in the study by frequency and severity.
Primary Efficacy Objectives	
 1. To characterize perception of mobility as measured by the PLUS-M while wearing the Revo-M compared to the everyday feet. 2. To characterize the level of activity restrictions as measured by the Trinity Amputation and Prosthesis Experience Scales Activity Restrictions subscale (TAPES-AR) while wearing the Revo-M compared to the everyday feet.

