The Revo-M prosthetic foot belongs to the group of energy-storage-and-release (abbrev: ESR) feet. It utilizes carbon springs and polyurethane-foam bumpers as elastic elements. These elastic elements allow for a harmonic rollover during stance phase. The proximal connection to other prosthetic components is provided by the aluminum upper part, which contains a pyramid adaptor for this purpose. Furthermore, there is a pivoting joint at the center of the foot within the aluminum upper part that combines with a tension element in the heel region to form a connection to the elastic elements of the foot.

Figure 2 CAD-rendered image of Revo-M without foot shell

Comparative Study Devices (Taleo and ProFlex XC)

Two commercially available comparative study devices will also be assessed in the study, the Taleo and the ProFlex XC. The comparative foot for transfemoral subjects will be the Taleo manufactured by Ottobock. The comparative foot for transtibial subjects will be the ProFlex XC manufactured by Össur.

Figure 3 Comparative Study Devices, Taleo (left) and ProFlex XC (right)

Study Device Technical Specifications

Table 1 Technical Specifications for the Three Study Devices

Specification	Revo-M (Investigational)	ProFlex XC (Comparative TT)	Taleo (Comparative TF)
Activity Levels	K2, K3 and K4	K3 and K4	K3
Max Body Weight	Size 26: 275 lbs (125 kg) Size 24: 220 lbs (100 kg)	365 lbs (165 kg)	330 lbs (150 kg)
Heel Height	Size 26: 10 mm Size 24: 20 mm	10 mm	Normal footshell (N) 10 +/- 5mm, Slim footshell (S) 15 +/- 5 mm
Footshell shape	Size 26: Normal Size 24: Slim	Normal	Normal (N), Slim (S)
Min. Clearance Height	Size 26: 112.5 mm (4 7/16") Size 24: 110 mm (4 1/3")	155 mm (6 1/8 ")	158 mm (6 1/4")
Sizes	24, 26 cm	22-24, 25-27, 28-30 cm	22 - 30 cm

Regulatory Classification

All study devices are Class I devices

FDA Registration under Device Listing Regulation number 890.3420 product code ISH.

Purpose

The purpose of the Revo-M Study is to characterize differences in performance and patient reported outcomes between the Revo investigational prosthetic foot and a comparative prosthetic foot (Taleo or Proflex XC) when compared to the control foot which is the subject's currently used energy storage and return (ESR) prosthetic foot. The data obtained from this study may also serve to evaluate the long-term performance of Revo.

Protocol

Study Summary

Period I

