The PROMIS Pain Interference – Short Form 4a has been incorporated into the patient journal. The patient will be asked six questions related to how pain may have interfered with certain activities in the last 7 days, and rate them on a 1-5 scale, with '1' being 'not at all' and '5' being 'very much.'

Study-specific Questionnaires

Subject Study-specific Questionnaire (Subject SSQ)

Questions have been developed to assess the end users' preferences regarding the three prosthetic feet.

Patient Journal

Subjects will be provided with a 'journal' to answer a questionnaire once per week during the accommodation period while wearing the current ESR foot and during home use while wearing the study devices. The weekly questionnaire in the journal will include questions about satisfaction with the prosthesis, positive and negative observations about prosthetic performance, medical issues, the use of pain medication and the PROMIS Pain Interference short form. The journals will be completed online using links that will be provided to subjects. In the case that a subject does not have easy access to the internet, paper journals will be provided. The journals will be reviewed together with the Investigator during in-person visits. In addition, subjects will also record in the journal any falls and resulting injuries. If any of the journal entries reveal complaints or adverse events, these will be reported on the Adverse Event form.

Training Requirements

The Investigator and investigational site personnel will be given training on the study requirements and an overview of the study devices prior to data collection for study patients. Training on the study requirements will include Investigator responsibilities and requirements, review of the study data collection protocol, review of the Electronic Data Capture (EDC) system with the paper and eCRF's, and study administration. The Investigator will also be responsible for completing Human Subject Protection Training that meets their IRB requirements at the initial review submission, if not already completed. In addition, the Investigator will be responsible for ensuring their certification, if required by the IRB, is current throughout the lifetime of the study, and will submit to the Sponsor a copy of the current certification each time it is renewed.

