 - results in medical or surgical intervention to prevent permanent impairment to body structure or a body function; or
3. led to fetal distress, fetal death or a congenital abnormality or birth defect.

Relatedness

Each adverse event will be assessed regarding relatedness to the study device or the fitting procedure. In addition, the level of relatedness will be classified according to definitions as presented in Table 3.

Table 3 Rating the Relatedness of Adverse Events

Relatedness:	Description:
Highly Probable	The adverse event follows a reasonable temporal sequence from receipt (or attempted receipt) of the device treatment or procedure.
Probable	The adverse event follows a reasonable temporal sequence from receipt of the device treatment or procedure and the possibilities of factors other than the device treatment or procedure, such as underlying disease, concomitant drugs, or concurrent treatment can be excluded.
Possible	The adverse event follows a reasonable temporal sequence from receipt of the device treatment or procedure and the possibility of device treatment or procedure involvement cannot be excluded. However, other factors such as underlying disease, concomitant medications, or concurrent treatment are presumable.
Unlikely	The adverse event has an improbable temporal sequence from receipt of the device treatment or procedure, or it can be reasonably explained by other factors, including underlying disease, concomitant medication, or concurrent treatment.
Not Related	The adverse event has no temporal sequence from receipt of the device treatment or procedure, or it can be explained by other factors, including underlying disease, concomitant medication, or concurrent treatment.

Severity Rating

The severity of adverse events will be classified according to definitions as presented in Table 4.

Table 4 Rating of the Severity of Adverse Events

Severity:	Description:
Mild	Usually transient, requiring no special treatment, does not interfere with the patient's daily activities.
Moderate	Low-level inconvenience or concern to the patient, may interfere with daily activities, usually resolved by simple therapeutic non-interventional methods.
Severe	Interruption in patient's daily activity requiring systemic drug therapy or other treatment.

Statistical Considerations and Data Analysis**Sample Size**

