The following risk-minimizing measures will be taken:

- The subjects will be individually fit by an experienced CPO and instructed to report to the CPO all the problems with the prosthesis. The CPO will be trained by Ottobock in the handling of the new prosthetic foot.
- The first steps with the new prosthesis will be deliberately accompanied by exercises which accelerate adaptive behavior and train proper behavior in critical situations.
- The subjects will be instructed that in case of any technical issues concerning the prosthesis, they should stop using it until the issue is resolved and to contact the investigational site to schedule further steps.
- The participants will be informed that they should refrain from performing any activity if they do not feel confident or safe.
- All activities during in-clinic tests will be performed under the close supervision of qualified personnel.
- The Revo-M investigational device used in the study has passed a fatigue test for 750,000 gait cycles corresponding to approximately 9 months of use.

The risks to subjects inherent in study procedures are limited to those associated with the six-minute walk test. Complications associated with this test include excessive fatigue, angina, or light-headedness. Subjects' blood pressure and resting heart rate will be measured prior to the test in accordance with recommendations from the American Thoracic Society (ATS Statement, 2002). Subjects will be encouraged to stop during the test if needed to catch their breath, and the test may be stopped by the investigator if subjects exhibit symptoms listed above.

Benefits

Subjects may or may not experience benefits such as improved walking performance during the course of the study while wearing the study devices. In any case, all subjects will need to return the study devices at the end of the study and return to using their existing ESR feet. However, the study

results may help the Sponsor identify ways to improve future versions of the Revo-M. In addition, by characterizing the comparative safety and effectiveness of the Revo-M (relative to both existing ESR feet and the two comparative study feet), society, the O&P industry, and the Investigators may also benefit from the knowledge gained.

Study Management

Sponsor Responsibilities

Sponsor responsibilities include:

1. Ensuring the study is designed and managed in compliance with all appropriate regulatory standards and is conducted according to the Study Protocol.

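### Adverse events are rated for relatedness to the study device or the fitting procedure but not to the everyday foot, so device-related events cannot be compared evenly between the Revo-M and the everyday foot

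*Combined protocol and SAP*

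**What the plan says.** The relatedness rule, under Adverse Events, Relatedness, in the combined protocol and SAP, is: "Each adverse event will be assessed regarding relatedness to the study device or the fitting procedure". Table 3 then grades relatedness, mainly by timing after receipt of the device or procedure and by whether other causes can explain the event.

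The everyday foot is kept apart from the study devices in several places:

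- The Study Devices row of the Clinical Study Summary reads "Revo-M, Taleo, and ProFlex XC prosthetic feet". The Control row is separate and reads "Current Energy Storing and Return prosthetic foot".
- Table 1, titled "Technical Specifications for the Three Study Devices", has columns for the Revo-M, ProFlex XC and Taleo only.
- The Patient Journal section says the journal is kept "while wearing the current ESR foot and during home use while wearing the study devices", which sets the two apart.

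The safety objective is "To characterize all device-related adverse events, stumbles, and falls experienced by subjects in the study by frequency and severity". It names no comparator. The Benefits section, however, expects society and the field to gain "by characterizing the comparative safety and effectiveness of the Revo-M (relative to both existing ESR feet" and the two comparative study feet).

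On collection, Adverse Event Reporting says: "Once a subject is enrolled, all adverse events must be reported until the subject is withdrawn or is terminated from the study". Falls are recorded in the journal, which is also kept on the everyday foot.

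**The concern.** The control condition fills two of the four home-use periods, and adverse events are collected in both. Yet the plan gives the rater no way to say that the foot on the subject's leg caused an event when that foot is the subject's own. The Revo-M can collect device-related events, while the foot it is set against in the Benefits section can hardly collect any.

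What is at stake is the reading of the safety tables. If device-related events are laid out by foot, an ordinary rate of foot-caused problems on the Revo-M would look like excess risk over the everyday foot. The section on interim analysis and adaptive design foresees carrying these subjects into a pivotal analysis, so the uneven rating could carry forward too. Causality is hard to reconstruct once the event has passed.

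**Working it through.** The plan states no figure on this point, so there is none to reproduce. The check is textual, with an illustration of size.

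**Step 1. What can be rated in each period**

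| Period | Foot worn | Can an event be rated related to the foot worn? | Other routes to a related rating |
|---|---|---|---|
| I | Everyday | No | On the wording, none: no study device has been received, and Table 2 marks no fitting at Visit 1 |
| II, III | Revo-M or comparative | Yes | The fitting at Visit 2 or 3; for Period III, also the earlier study foot |
| IV | Everyday | No | The refitting at Visit 4, or a study foot worn earlier |

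Two details bear on Period I. Enrollment includes an alignment check of the current foot, with minor changes allowed; a site might count that as a fitting procedure, but the rating would still not be to the foot. Separately, the Adverse Event Definition makes underlying disease, and its symptoms, non-reportable if present before study devices are fitted. That may remove some Period I events altogether.

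In Period IV, tying an everyday-foot event to an earlier study foot would move it into the Revo-M or comparative-foot count.

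**Step 2. Which comparisons are affected**

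Revo-M versus Taleo or ProFlex XC: all three are study devices under the same rule, so the rule creates no asymmetry. Revo-M versus everyday foot: only the first can be rated related to itself.

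**Step 3. Size, as an illustration**

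- n = 24, the minimum in Sample Size.
- p = true risk of a foot-caused event per subject per 8-week period, taken as equal on every foot. The documents give no value; 5% to 30% is assumed.

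Expected Revo-M subjects with a related event = n × p. The true difference per 8-week period is p − p = 0. The rated difference is p − 0 = p.

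| Assumed p | Revo-M, 24 × p | Rated related to the everyday foot, per period | False difference |
|---|---|---|---|
| 5% | 1.2 | about 0 | 5 points |
| 10% | 2.4 | about 0 | 10 points |
| 20% | 4.8 | about 0 | 20 points |
| 30% | 7.2 | about 0 | 30 points |

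If some raters apply Table 3 to whatever foot is being worn, and so capture a fraction f of everyday-foot events, the false difference shrinks to p × (1 − f).

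**Step 4. Exposure**

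Four periods of about 8 weeks make 4 × 8 = 32 weeks: 2 × 8 = 16 on the everyday foot, 8 on the Revo-M and 8 on the comparative foot. Raw counts by foot would not be comparable even under an even rating rule, so Step 3 is stated per 8-week period.

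**The case against.** The strongest reply is that the plan never promises this comparison as a result. The safety objective names no comparator, whereas the primary and secondary efficacy objectives all name the everyday feet. Data Analysis summarizes events by frequencies and percentages, with no between-foot safety test. Comparative safety appears only in the Benefits section, as knowledge that may be gained. This stands, and it limits the point to a descriptive comparison.

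A second reply is that an even comparison is still possible. All adverse events are reported from enrollment whatever their cause, and falls are recorded on the everyday foot too. The objective's wording does not make clear whether the device-related condition also restricts stumbles and falls. This also stands, but the plan does not specify an all-cause summary by foot worn, and the objective is framed around device-related events.

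A third reply is that Table 3 speaks only of the device, so a rater might apply it to the foot being worn. Some might. The sentence introducing the rating says study device, however, and different readings across up to five sites would give inconsistent ratings.

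A reader might infer something stronger: that no event on the everyday foot can ever be device-related, that half of follow-up is therefore empty by construction, and that the trial's comparative safety result is biased. The documents do not support that. Period IV events can be rated related to the refitting or to an earlier study foot, and no comparative safety result is defined that could be biased.

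**Conclusion.** The point holds as a gap in the rating rule. An event caused by the everyday foot cannot be rated related to that foot, so a descriptive comparison of device-related events between the Revo-M and the everyday foot is uneven, to the Revo-M's disadvantage.

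The false difference equals the true foot-caused risk, on three assumptions: that risk is the same on every foot, raters follow the wording, and the comparison is per 8-week period. The 5% to 30% range is assumed, not drawn from the documents. No planned test or stated figure changes, and the efficacy analyses are untouched. This is a cheap improvement worth making, not a flaw that undermines the trial.

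**What to change.** In Relatedness and Table 3, rate each event for relatedness to the foot worn at onset (everyday, Revo-M or comparative) and to that foot's fitting or alignment, with the same scale in all four periods.

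In Data Analysis, tabulate both related and all-cause adverse events, stumbles and falls by foot worn, per unit of exposure (about 16 weeks everyday, 8 Revo-M, 8 comparative). Relatedness remains a judgement, so the all-cause table should stand beside the related one. State whether the device-related condition in the safety objective also covers stumbles and falls.

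The cost is a wording change and at most one added field on the Adverse Event form. That form is not in the documents, so it cannot be checked whether it already records the foot worn. No added visits are needed.
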